The intervention of this study will require participants to perform body-weight HIIT in their own home environment. Each participant's safety and suitability for engagement in such exercise will be assessed rigorously during the initial screening and baseline exercise testing. If any concerns become apparent at this stage then the participant will be removed from the study on the basis of their safety. Whilst exercising at home, participants will be provided with a list of concerning symptoms to be aware of, and advised to contact emergency services immediately if these symptoms were to develop. In addition, we will suggest to participants that they have another person in the near vicinity when performing their HIIT sessions – particularly for the initial sessions.

Stopping rules and discontinuation

The safety of participants is of utmost importance to our study group. Participants' continuation in the study would be deemed unsuitable if they were to develop any persistent, uncomfortable or clinically significant symptoms in response to any elements of the intervention(s) or procedures. Alongside the participants' right to withdraw from the study whenever they choose, the study team reserves the right to discontinue a participant's involvement if the Chief Investigator decides that continued involvement is not in their best interests. The basis of this decision will be discussed with the participant to achieve a mutually agreed outcome.

There are some criteria that would warrant immediate removal from the study, to ensure the safety of the participants in relation to the exercise element of this study. In particular, immediately removal will be considered if a participant were to develop any of the following symptoms during any exercise sessions (CPET or HIIT):

- Chest pain or tightness,
- Palpitations,
- Faintness,
- Sudden pallor,
- Loss of co-ordination,
- Confusion,
- Dizziness, or
- Excessive breathlessness

Participants will be given lay language information detailing these symptoms to ensure that they are aware of them at all times, especially when performing the HIIT sessions in their home environment.

In addition, as participants will be monitored during their CPET sessions, they will also be observed for the following signs:

- Changes on continuous ECG monitoring suggestive of ischaemia (e.g. >2mm ST depression) or arrhythmia
- Systolic blood pressure rising >250mmHg
- Diastolic blood pressure rising >120mmHg

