- Blood pressure drop of >20mmHg
- Drop in heart rate >10 beats per minute
- Oxygen saturations <94%

If any of these were to occur during the CPET session then this will also be grounds for removal from the study to ensure the safety of the participants.

Participants will also be encouraged to report any injuries that occur during the exercise sessions. With all injuries, a discussion will be held to determine whether removal is appropriate, however, in the case of any injuries that requires medical intervention, an individual's participation will be discontinued.

RANDOMIZATION AND BLINDING

Participants will be recruited to the study by the Co-Investigator [name] and the Chief Investigator [name]. All participants will go through an initial screening appointment and then a final decision regarding recruitment will be made after discussion between the study investigators. Following this, they will be randomised to either the intervention or control groups by [name] using the online "Sealed Envelope" software (www.sealedenvelope.com), which is the standard method of randomisation utilised for studies in this research department. The randomisation ratio will be 1:1 and the allocation

sequence will be generated by an algorithm within the online software, and as such, will be third party.

This study will be investigating the effects of an exercise intervention. Due to the nature of this intervention and the processes required to safely monitor the intervention group, blinding of participants or study investigators will not be possible. However, any research staff involved solely in data analysis will be blinded to the group that participants are allocated to. Neither those involved in data analysis, nor the study statistician will have contact with participants.

Maintenance of randomisation codes and procedures for breaking code

Blinding of participants and research staff is not possible in this study, therefore will not be used. Thus, there will not be any randomisation codes and no need to break a randomisation code. In the event of an SAE, the group in which the participant has been allocated to will be easily accessible from the study master file, which can be accessed by the Chief Investigator or any of the Co-Investigators.

TRIAL/STUDY MANAGEMENT

The trial will be managed by a single assigned project manager. There will not be a Trial Steering Committee, Management Group or Data Monitoring Committee for this.

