- Completed the NHS Path to Remission programme and achieved diabetes remission (HbA1c <48mmol/mol (6.5%), and off diabetes medications for at least three months)

Exclusion criteria

- BMI > 40kg·m²
- Current participation in a formal exercise regime
- Current pregnancy or breastfeeding
- Uncontrolled hypertension (blood pressure >160/100mmHg)
- History of cardiovascular disease:
 - Symptomatic angina
 - Heart failure (class III/IV)
 - Significant arrhythmias
 - Right to left cardiac shunt
 - Recent acute coronary syndrome
 - Severe aortic valvular disease
 - Active cardiac infection
- Background of the following respiratory diseases:

- Pulmonary hypertension
- Significant COPD
- Uncontrolled asthma
- History of malignancy undergoing current treatment or palliation
- Presence of significant musculoskeletal, neurological or cerebrovascular disease
- Any other medical condition deemed by the investigators to preclude inclusion into the study

These exclusion criteria are based on the contraindications listed in the American Thoracic Society / American College of Chest Physicians statement on CPET (ATS/ACCP, 2003).

Expected duration of participant participation

Study participants will be participating in the study for 16 weeks.

Removal of participants from therapy or assessments/Participant Withdrawal

Participants may be withdrawn from the trial either at their own request or at the discretion of the Investigator. The participants will be made aware that this will not affect their future care. Participants will be made aware (via the information sheet and consent form) that should they withdraw the data collected to date cannot be erased and may still be used in the final analysis.

Participants may be removed temporarily or permanently depending on the prevailing circumstances around the time of the decision. Grounds for temporary removal from the study include (but are not limited to):

- very mild joint or limb injury (not requiring medical attention)
- inability to continue with the exercise intervention due to unforeseen personal circumstances (e.g. bereavement)

Participants will be permanently removed from the study in the following situations:

- withdrawal of consent
- significant injury (requiring medical attention)
- development of any high-risk symptoms (listed above in the Exclusion Criteria section) whilst performing any of the home-based exercise sessions
- evidence of high-risk signs (listed above) during the CPET sessions

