- failure to achieve minimum compliance with the exercise intervention

If a participant withdraws their consent after screening but before the first study visit, they may be replaced. Should a participant withdraw during or following the first study-visit, they will not be replaced, and instead, will be deemed to have dropped out of the study. As randomisation will occur immediately before the participant's first study visit, anyone who withdraws after randomisation will also be classed as a drop-out from the study.

For participants that are removed from the study, details of this decision will be documented in the CRF. The date and time of removal will be documented, as well as the reason for doing so (if provided). A decision to remove any participant that is made by the research team, will be discussed with the Chief Investigator and will require final agreement by them. We do not envisage any potential issues with abrupt withdrawal from the study and therefore, do not have measures to prevent any issues. Participants that are withdrawn will be advised to continue their care arrangements with their General Practitioner, and a letter will be sent to the General Practitioner informing them of the individual's participation in the study – in the same way as for all participants who complete the study.

Informed consent

All participants will provide written informed consent. The Informed Consent Form will be signed and dated by the participant before they enter the trial. The Investigator will explain the details of the trial and provide a Participant Information Sheet, ensuring that the participant has sufficient time to consider participating or not. The Investigator will answer any questions that the participant has concerning study participation.

Informed consent will be collected from each participant before they undergo any interventions (including physical examination and history taking) related to the study. One copy of this will be kept by the participant, one will be kept by the Investigator, and a third will be retained in the patient's hospital records.

Should there be any subsequent amendment to the final protocol, which might affect a participant's participation in the trial, continuing consent will be obtained using an amended Consent form which will be signed by the participant.

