All adverse events will be assessed for seriousness, expectedness and causality. A distinction is drawn between serious and severe AEs. Severity is a measure of intensity, whereas seriousness is defined using the criteria above. Hence, a severe AE need not necessarily be serious.

Causality

Not related or improbable: a clinical event including laboratory test abnormality with temporal relationship to the study intervention which makes a causal relationship incompatible or for which other treatments, chemicals or disease provide a plausible explanation. This will be counted as “unrelated” for notification purposes.

Possible: a clinical event, including laboratory test abnormality, with temporal relationship to the study intervention which makes a causal relationship a reasonable possibility, but which could also be explained by other interventions, chemicals or concurrent disease. This will be counted as “related” for notification purposes.

Probable: a clinical event, including laboratory test abnormality, with temporal relationship to the study intervention which makes a causal relationship a reasonable possibility, and is unlikely to be due to other interventions, chemicals or concurrent disease. This will be counted as “related” for notification purposes.

Definite: a clinical event, including laboratory test abnormality, with temporal relationship to the study intervention which makes a causal relationship a reasonable possibility, and which can definitely not be attributed to other causes. This will be counted as “related” for notification purposes.

With regard to the criteria above, medical and scientific judgment shall be used in deciding whether prompt reporting is appropriate in that situation.

Reporting of adverse events

Participants will be asked to inform the research team of any adverse event occurring. The participant may choose to contact the team themselves, or inform us when a member of the research team performs one of the regular scheduled contacts with the participant. All adverse events will be recorded and closely monitored until resolution or stabilisation, even if it is unlikely that the study intervention is not the cause. The Chief Investigator shall be informed immediately of any adverse events, and shall determine seriousness and causality, in conjunction with other clinically-trained research staff and any treating medical practitioners.

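### Events that end participation during home HIIT may be reported at the next scheduled contact, and the protocol does not tell participants to suspend HIIT or alert the team at once

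*Protocol*

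**What the plan says.** **Removal.** Protocol, Stopping rules and discontinuation, lists symptoms such as chest pain, palpitations, dizziness and excessive breathlessness, and says "immediately removal will be considered if a participant were to develop any of the following symptoms during any exercise sessions (CPET or HIIT"). The same section discontinues participation "in the case of any injuries that requires medical intervention". Under Removal of participants from therapy or assessments, the lead-in is firmer: "Participants will be permanently removed from the study in the following situations". One of the situations is "development of any high-risk symptoms (listed above in the Exclusion Criteria section) whilst performing any of the home-based exercise sessions". A removal decision made by the team "will be discussed with the Chief Investigator and will require final agreement by them".

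**Reporting to the team.** Protocol, Adverse Events, Reporting of adverse events, begins: "Participants will be asked to inform the research team of any adverse event occurring". It then names two routes, in that each person "may choose to contact the team themselves, or inform us when a member of the research team performs one of the regular scheduled contacts". The Chief Investigator is then to be told of any adverse event immediately.

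**Medical care.** Under Safety endpoints, participants exercising at home are "advised to contact emergency services immediately if these symptoms were to develop". Intervention Period also requires immediate medical attention for the listed symptoms, from emergency services or the General Practitioner. The adverse-event definitions repeat the instruction for symptoms of the main risks of HIIT.

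**Contact.** For the HIIT group, Intervention Period sets a minimum of weekly contact for 4 weeks and two-weekly contact after that. Compliance says at least weekly, without a change at week 4.

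**The concern.** A removal rule for unsupervised exercise can act only once the team knows of the event. The reporting rule lets every adverse event wait for a scheduled call, including those that the protocol treats as ending participation. The duty to inform the Chief Investigator at once does not shorten that wait, because it starts when the team learns of the event.

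Other provisions do not clearly close the gap. The study mobile number is offered for queries and concerns, but its use is optional. The exercise documentation pack records problems but does not send them to anyone. Injury reporting is encouraged, with no time limit. The General Practitioner is told that the patient is in the study, but is not asked to alert the team.

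A participant could therefore seek care as instructed, follow the reporting rule, and do further home sessions aimed at more than 85% of maximum heart rate before anyone applies the removal rule. The trial has no Data Monitoring Committee and the sessions are unsupervised, so prompt reporting by the participant is what makes this rule work.

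**Working it through.** The protocol states no figure on this point, so the check is a comparison of its sections and a count of sessions.

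**Step 1: what must happen after a listed symptom at home.**
- Seek medical care: immediate (Safety endpoints; Intervention Period; adverse-event definitions).
- Tell the research team: own contact or the next scheduled one, with no deadline (Reporting of adverse events).
- Suspend later HIIT sessions: not stated anywhere in the protocol.
- Removal: to be considered (Stopping rules) or permanent (Removal of participants), with the Chief Investigator's final agreement for decisions made by the team.

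**Step 2: inputs for the session count.**
- 3 HIIT sessions per week for 16 weeks (Intervention Period).
- 4 sessions in a week that follows a missed session (Compliance).
- Contact gap of up to 1 week under Compliance, or up to 2 weeks after week 4 under Intervention Period alone.

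**Step 3: further sessions before the next contact.** The formula is sessions in the gap minus the symptomatic one. It is an upper bound, because it puts the symptomatic session first after a contact.
- Weekly contact: 3 − 1 = 2. With a catch-up: 4 − 1 = 3.
- Two-weekly contact: 2 × 3 − 1 = 5. With one catch-up: 4 + 3 − 1 = 6.

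Both contact rules are minimums, so weekly contact satisfies both. The firm bound is therefore 2 (3 with a catch-up). The larger figures need the Compliance section to be disregarded.

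**Step 4: scale.** The HIIT arm has 20 / 2 = 10 participants, each with 16 × 3 = 48 planned sessions.

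**Step 5: contacts needed if weekly contact is fixed.**
- Intervention Period minimum: 4 + 12/2 = 10 per participant.
- Compliance minimum: 16 per participant.
- Difference: 16 − 10 = 6 per participant, or 6 × 10 = 60 over the arm.

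**The case against.** The reporting rule is general. It covers any adverse event in either arm, asks for reports, and names two channels. It does not tell anyone to wait, and does not say that HIIT may go on meanwhile. The rule specific to the listed symptoms is to seek immediate medical attention. That interrupts the session and usually puts a clinician, often one who knows of the trial, between the event and the next session. A second person nearby is also suggested. Symptom instructions belong in the lay information and the exercise documentation pack, which are not shown.

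Much of this stands. The acute risk is covered, and the pack may already say more. It does not remove the point, because the stated reporting rule, followed as written, can delay the stated removal rule, and nothing in the protocol makes an exception.

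Four stronger readings are tempting and are not supported:
- *A participant with symptoms is left without care.* Three sections require immediate care.
- *Five or six further sessions are to be expected.* That holds only if two-weekly contact is followed alone after week 4, and it is an upper bound even then.
- *The probability of harm can be put in figures.* The documents give no rate for the listed symptoms. If 1% to 10% of participants are assumed to have one, the chance of at least one among 10 is 1 − 0.99^10 = 0.096 to 1 − 0.90^10 = 0.651. That is the chance of a symptom, not of exercising again before the team knows, which can be no larger and cannot be estimated here.
- *There are three conflicting removal rules.* The discretion to withdraw a participant after any adverse event is general, and on an ordinary reading it yields to the specific symptom rule. The real difference is between considered and permanent removal.

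**Conclusion.** The point holds in limited form. The protocol ends participation for certain events during home HIIT (or, in one section, considers ending it), yet lets those events be reported at the next scheduled contact. It contains no instruction to suspend later sessions or to tell the team at once. The consequence is up to about 2 further unsupervised sessions (3 with a catch-up) with weekly contact, and up to 5 (6 with a catch-up) only on the two-weekly minimum alone after week 4.

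This assumes that the symptomatic session falls first after a contact, that the participant keeps to the session schedule, and that no clinician advises a pause. It concerns what the protocol requires, not what participants may be told in material that is not shown. How often it would happen cannot be derived from the documents, and the protocol describes the incidence of HIIT-related musculoskeletal and cardiovascular events as very low.

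Three smaller defects bear on the same rule: the two contact schedules differ, the removal wording differs between two sections, and the symptom cross-reference points to the exclusion criteria although the list is under Stopping rules.

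**What to change.** In Reporting of adverse events and in the exercise documentation pack, state that a participant with a listed symptom during HIIT, or an injury needing medical attention:

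1. stops HIIT;
2. seeks care as already instructed;
3. calls the existing study number the same day;
4. does not resume until the team has reviewed the event and the Chief Investigator has decided on removal.

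Limit reporting at scheduled contacts to other adverse events.

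At the same time:
- state weekly contact for the HIIT arm in both Intervention Period and Compliance;
- point the symptom cross-reference under Removal of participants to the Stopping rules list;
- give one removal rule in both sections. Whether removal is mandatory or considered is for the Chief Investigator to choose.

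**Cost.** No new equipment, and a few more participant calls. Weekly contact adds up to about 60 contacts in total if the two-weekly schedule would otherwise have been followed, and none if contact is already weekly. Because this changes a safety rule, ethics committee review and updated participant material are probable, and renewed consent from enrolled participants is possible. Mandatory removal has its own price: the list includes symptoms as broad as dizziness, participants are not replaced after the first study visit, and one loss is 1 of about 10 in the arm.
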